	• SpyScope TM DS Access and Delivery Catheter is intended to provide direct visualization and to guide both optical and accessory devices for diagnostic and therapeutic applications during endoscopic procedures in the pancreatico-biliary system including the hepatic ducts.								
	 The following devices will be available upon commercialization: SpyScopeTM DS II Access and Delivery Catheter is intended to provide direct visualization and to guide both optical and accessory devices for diagnostic and therapeutic applications during endoscopic procedures in the pancreatico-biliary system including the hepatic ducts. SpyGlassTM Retrieval Basket is indicated for the endoscopic removal of stones, stone fragments, or foreign bodies in the pancreaticobiliary system. 								
Device	SpyGlass [™] Digital System								
Study Design	 Prospective Consecutive cases Multi-center Randomized 1:1 ratio: Group A (ERC arm): Clearance of bile duct stones using standard-of-practice ERCP techniques Group B (DSC arm): Clearance of bile duct stones using DSC techniques 								

E7131 -	– Non-Complex Biliary Stones DSC vs ERC RCT						
	 Block-randomization by site Non-inferiority hypothesis Validation of stone clearance by ERC in DSC arm and by DSC in ERC arm. 						
Number of Subjects	 250 subjects An additional 5 Roll-in cases. Each participating endoscopist at each of the participating centers must perform 5 Roll-in cases. These roll-in cases will not count towards the enrollment ceiling of 250 cases. Procedures to be conducted only by the Principal Investigator. Sub-Investigators will be authorized to do study procedures only on an exception basis. Such exception may be granted by the Sponsor in consultation with the Principal Investigator of the site and Lead Principal Investigator to the study. 						
Number of Sites	Up to 15 global sites						
Primary Endpoint	Complete stone clearance by extraction of bile duct stones from the common bile duct (CBD) into duodenum as determined by fluoroscopy free cholangioscopy in the DSC arm and by cholangiography in the ERC arm.						
Secondary Endpoints	1. Evaluation of all serious adverse events (SAEs) including all deaths (related and unrelated), severity, onset, time to resolut related to the DSC devices and/or procedure and/or the ERC procedure through 30 days post procedure.						

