4.1. Primary Endpoint

The primary endpoint is complete stone clearance by extraction of bile duct stones from the common bile duct (CBD) into duodenum by fluoroscopy free cholangioscopy in the DSC arm and by cholangiography in the ERC arm.

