- 5. Use of needle-knife other than for visibly impacted stones will be considered a **cannulation failure.** Patients will be followed through 30 days post index procedure as indicated in the follow-up schedule.
- After cannulation succeeds, number and estimated size of biliary stones will be confirmed following contrast injection. Biliary sphincterotomy will be performed. Additional papillary large balloon dilation can be performed if the sphincterotomy is felt to be inadequate.
- 7. Stone removal using standard techniques. If unexpectedly large stones are encountered, papillary large balloon dilation or mechanical lithotripsy may be applied.
- 8. If stone clearance fails due to size/shape of the stone(s), **stone extraction failure** will have occurred. However, participating institutions may proceed with their standard of care interventions at this point, including cholangioscopy and EHL/LL or stent placement with repeat ERC on another day. Patients will be followed through 30 days post index procedure as indicated in the follow-up schedule.

Post ERC validation by DSC:

- 9. In patients in whom stone extraction is deemed to be complete, the SpyGlass[™] cholangioscope will then be advanced to confirm complete clearance of the bile duct.
- 10. If residual stone(s) are noted, then additional balloon sweeps, and/or stone retrieval using a SpyGlassTM Retrieval Basket, of the bile duct will be performed with fluoroscopy assistance and supplemented by papillary large balloon dilation, mechanical lithotripsy and EHL/LL as needed.
- 11. The number of "missed stones" equal to or greater than 5 mm in size per endoscopist's estimate will be documented.

In Group B (DSC arm):

- 1. Needle knife pre-cut sphincterotomy may be utilized for stones visibly impacted at the ampulla.
- 2. Fluoroscopy-free cannulation technique to gain biliary access for all other patients.
 - Do not prime the sphincterotome with contrast.
 - Following deep cannulation, confirm free advancement of the guidewire into a ductal system.

- Aspiration of bile via the sphincterotome using a syringe to confirm bile duct cannulation.

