- 15. Stones visualized at cholangioscopy may also be captured and retrieved sequentially using the SpyGlass[™] Retrieval Basket, commencing distally and progressing proximally to the hilum as with balloon extraction. Extracted stones will be counted. If stone capture is difficult using the basket, the endoscopist may switch to balloon extraction at any point. Where retrieval is successful using purely SpyGlass[™] Retrieval Basket alone (without need for balloon catheter), or if retrieval using SpyGlass[™] Retrieval Basket is utilized for the final visualized stone, saline irrigation (Step 12) and cholangioscope reinsertion (Steps 13/14) will not be necessary.
- 16. EHL or LL may be performed for unexpectedly large/complex stones.
 - If stone clearance fails due to size/shape of the stone(s), electro-hydraulic lithotripsy (EHL) or laser lithotripsy (LL) can be performed.
 - If stone clearance still fails **stone extraction failure** will have occurred. However, participating institutions may proceed with their standard of care interventions at this point, including ERC with mechanical lithotripsy or stent

placement followed by repeat ERC on another day. Patients will be followed through 30 days post index procedure as indicated in the follow-up schedule.

Post DSC validation by ERC:

- 17. An occlusion cholangiogram will be performed using the stone extraction balloon catheter and presence or absence of filling defects will be documented.
- 18. If filling defects are noted, then balloon sweeps of the bile duct will be performed to determine if the filling defects are "missed" bile duct stones or simply air bubbles.

The number of "missed stones" > 5 mm per endoscopist's estimate will be documented.

8.7. 24-Hour, 7-Day, and 30-Day Follow-up

The following data will be collected for all subjects (including Roll-in cases) during these follow up periods:

- Phone call to patient
- Serious Adverse Events, all events of Cholangitis, Pancreatitis, Perforation, and Bleeding, and Device Events, including discharge summaries for any device-related hospitalizations.

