9.1.2. Sample Size

The sample size was estimated based on the following assumptions:

- Expected stone clearance rate of 90% in DSC-guided and ERC-guided group
- Non-inferiority margin: 10%
- Alpha (1-sided): 0.05
- Power: 80%

With the above assumptions, a sample of 250 patients (125 in each arm) is needed to detect the non-inferiority of the clearance rate in the DSC arm compared to the ERC arm. This sample size was calculated using StatXact 9[®].

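### Protocol 8.6 counts a residual stone estimated at exactly 5 mm as missed in the ERC arm but not in the DSC arm, which would tilt any between-arm report of missed stones.

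*Protocol*

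**What the plan says.** The Protocol Synopsis lists cross-checking by the other modality as a design feature: "Validation of stone clearance by ERC in DSC arm and by DSC in ERC arm". Section 8.6 gives the operating rules.

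- **ERC arm (Group A, steps 9 to 11).** Once extraction is judged complete, the cholangioscope is advanced to confirm clearance. Residual stones are swept or retrieved. The number of missed stones "equal to or greater than 5 mm in size per endoscopist" (by that person's estimate) is documented.
- **DSC arm (Group B, steps 17 and 18 and the sentence after them).** An occlusion cholangiogram is done and filling defects are recorded as present or absent. If there are any, sweeps show whether they are stones or air bubbles. The number of missed stones "> 5 mm per endoscopist" (again an estimate) is documented.

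No other text in the protocol defines a missed stone, and the SAP does not mention missed stones. The primary endpoint rests on each arm's own modality: "by fluoroscopy free cholangioscopy in the DSC arm and by cholangiography in the ERC arm" (Protocol 4.1; the Synopsis and SAP 3.1 agree).

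**The concern.** One limit includes 5 mm and the other excludes it. The same finding is therefore recorded differently by arm, and the difference runs one way, towards fewer recorded misses in the DSC arm.

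The boundary case is plausible. Sizes are estimated by eye in an unblinded trial (Protocol 8.5), and estimates may settle on round values such as 5 mm.

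What is at stake is the credibility of the cross-validation. Because each arm's clearance is judged by its own method, a reader asking whether a duct declared clear in one arm is as clear as in the other will look at the missed-stone counts. Those counts should not differ merely because of a definition.

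**Working it through.** **Step 1. The two rules side by side.**

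| Estimated size of residual stone | ERC arm (5 mm or more) | DSC arm (more than 5 mm) |
|---|---|---|
| below 5 mm | not counted | not counted |
| exactly 5 mm | counted | not counted |
| above 5 mm | counted | counted |

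The arms differ in the middle row only.

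**Step 2. Does the count enter any planned result?** The places checked were the primary endpoint (Protocol 4.1, SAP 3.1), the three secondary endpoints (Protocol 4.2, SAP 5.1), the hypotheses, sample size and test (Protocol 9.1.1 to 9.1.3, SAP 3.1.1 to 3.1.3), and the subgroup, pooling, multivariable and learning-curve analyses (SAP 5.6 to 5.9). None uses missed stones, and no text turns a missed stone into a clearance failure.

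**Step 3. The plan's own figure.** Protocol 9.1.2 takes 90% clearance in both arms, a 10-point margin, one-sided alpha 0.05 and 80% power, and arrives at 125 per arm. An exact unconditional non-inferiority test ordered by the restricted-likelihood (Farrington-Manning) score gives 81.7% power at 125 per arm, with maximum type I error 0.0495. Of the sizes tried, 124 per arm was the smallest to reach 80% (80.5%). The stated 250 is reproduced, and no input to it depends on the missed-stone limit.

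**Step 4. How large could the tilt be?** The documents give no sizes for residual stones, so this is illustration only. Assume the same true situation and equal detection in both arms. Let r be the share of randomised patients with a residual stone recorded above 5 mm, and q the share with one recorded at exactly 5 mm and none larger.

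- Recorded rate in ERC = r + q
- Recorded rate in DSC = r
- Artificial difference = (r + q) − r = q

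With 125 patients per arm:

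| Assumed q | Extra ERC patients recorded | Artificial difference |
|---|---|---|
| 1% | 125 × 0.01 = 1.25 | 1 point |
| 2% | 125 × 0.02 = 2.5 | 2 points |
| 5% | 125 × 0.05 = 6.25 | 5 points |

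Counting stones instead of patients, suppose recorded sizes were spread evenly over the whole numbers 5 to 10 mm. Then 1/6 = 16.7% of the stones counted in ERC would go uncounted in DSC. If half were called 5 mm, it would be 50%. Both distributions are assumptions.

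**Step 5. Could a common limit be applied afterwards?** The data list in Protocol 8.6 collects the number and approximate size of extracted stones for all subjects. Residual stones found at validation are themselves swept or retrieved (Group A step 10, Group B step 18), so their sizes may be in the database. The list does not say whether they are included, or whether they are recorded apart from stones removed earlier. Recovery is possible but not assured.

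**The case against.** The strongest reply is that this is most likely a drafting slip of one character in a count that no planned analysis uses. Much of that stands, and it rules out several stronger readings.

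- **A reader might infer that the primary comparison is biased.** The documents do not support this. Each arm's own modality decides clearance, and step 2 found no route from a missed stone to an endpoint.
- **A reader might infer that this is the trial's only check on clearance.** It is not. Filling defects are documented in the DSC arm without a size limit, and biliary re-interventions are collected in both arms at 24 hours, 7 days and 30 days and when unscheduled (Table 8.1-1). Neither gives a like-for-like count of residual stones by arm, so the mismatch still matters.
- **A reader might infer that the discrepancy cannot be undone.** Step 5 shows that this is not established.
- **A reader might infer that different limits were intended.** Nothing in either document gives a reason for them.

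It is also fair to object that the arms would not be comparable even with one limit. ERC cases are checked by direct cholangioscopy. DSC cases are checked by an occlusion cholangiogram, with sweeps only if a defect is seen. Detection and size estimation therefore differ anyway. This stands in full: it limits what a common limit can achieve, but it does not justify two limits.

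Finally, the DSC side of the point rests on a single sign, which can change when text is taken from a PDF. The less-than-or-equal sign in Protocol 6.2 (inclusion criterion 4) and the greater-than-or-equal sign in Table 22.2-1 (hemorrhage) are intact, which makes a misreading less likely but does not exclude it.

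**Conclusion.** As the protocol reads, a residual stone estimated at exactly 5 mm is counted in the ERC arm and not in the DSC arm, and nothing in either document reconciles the two rules. The effect on the primary endpoint, the listed secondary endpoints, N and power is nil.

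Any between-arm report of missed stones would be tilted towards DSC. The documents do not allow the size of the tilt to be estimated. The 1-to-5-point range rests on assumed shares of patients with a 5 mm stone and on equal detection in both arms. If detection differs, the observed gap could be larger, smaller or reversed, but the definitional part of it still favours DSC.

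The conclusion depends on the sign in the DSC text being as printed. If the original page shows the inclusive sign, the discrepancy disappears. Otherwise it is a small defect in a data-collection rule, worth correcting because the correction is nearly free.

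**What to change.** 1. Check the sign in the sentence after Group B step 18 against the original protocol page.
2. If it differs from Group A step 11, reconcile the two to one limit in identical words. The documents do not show which was intended, so the sponsor must choose.
3. Have the eCRF record the number and estimated size of stones found at validation, separately from those removed earlier, so that the same limit is applied by program in both arms.
4. Wherever missed stones are reported by arm, note that the arms were validated by different modalities, so a common limit removes the difference in definition but not in detection.

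The cost is one protocol sentence and one eCRF field. No procedure, visit or sample-size change is needed, because the stones are already seen, sized by eye and removed.

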8.8. Study Completion

Subjects will be followed for 30 days post-index procedure. At study completion, an End of Study form will be completed, indicating whether the subject completed the study. If the last follow-up visit was not completed, the investigator will note the reason on the study completion form (e.g. subject withdrawn by investigator, subject withdrew consent, lost to follow-up, SAE, death, etc.).

9. Statistical Considerations

9.1. Primary Endpoint

Preliminary DSC-guided stone clearance rate was established in a pilot study¹ and found to be comparable to that of ERC-guided stone clearance. Eight relevant peer reviewed publications²⁻⁹ reporting on ERC-guided biliary stone clearance rates representing 2721 patients were analyzed. A meta-analysis was conducted of the biliary stone clearance rates, yielding a point estimate of 90% with a 95% CI of [85%, 94%].

9.1.1. Hypotheses

We hypothesize that the DSC-guided stone clearance rate is non-inferior to that of the ERCguided stone clearance rate. We assume a DSC-guided and ERC-guided stone clearance rate of 90% with a 10% non-inferiority margin. The following hypothesis will be tested:

H₀: P_{DSC} minus P_{ERC} \leq - Δ (Inferior)

H₁: P_{DSC} minus P_{ERC} > - Δ (Non-inferior)

where P_{DSC} and P_{ERC} are the stone clearance rates for the DSC arm (test) and the ERC arm (control), respectively, and (Δ delta) is the non-inferiority absolute margin.

9.1.2. Sample Size

The sample size was estimated based on the following assumptions:

- Expected stone clearance rate of 90% in DSC-guided and ERC-guided group
- Non-inferiority margin: 10%
- Alpha (1-sided): 0.05
- Power: 80%

With the above assumptions, a sample of 250 patients (125 in each arm) is needed to detect the non-inferiority of the clearance rate in the DSC arm compared to the ERC arm. This sample size was calculated using StatXact 9[®].

9.1.3. Statistical Methods

An exact test will be used to test the non-inferiority hypothesis of the DSC-guided vs. ERC-guided stone clearance rates.

9.2. Analysis Populations

9.2.1. Enrolled Cohort

A subject is considered enrolled after signing the study-specific Informed Consent Form (ICF). Patients who sign the ICF but subsequently do not meet one or more of the selection criteria will be considered screen failures and will be excluded from the study.

9.2.2. Intent-to-Treat Cohort (ITT)

This cohort consists of those enrolled patients who meet all inclusion/exclusion criteria and are subsequently randomized.

9.2.3. Per-Protocol Cohort (PP)

The per-protocol cohort is a subset of the ITT subjects who are treated per protocol post randomization with no major protocol deviations (ICH E9 definitions).

9.3. Data Analyses

9.3.1.Baseline

Baseline data will be summarized using but not limited to the following variables: subject demographics, medical history, and history of prior ERCP or sphincterotomy. Descriptive statistics (e.g., mean, standard deviation, n, minimum, maximum) will be reported for continuous variables and frequency tables for discrete variables.

9.3.2. Procedure Data

Procedure data, such as cannulation success, biliary sphincterotomy and stone removal will be collected and reported using descriptive statistics (e.g., mean, standard deviation, n, minimum, maximum) for continuous variables and frequency tables for discrete variables.

9.3.3. Post-Procedure Data

Post-procedure data will be collected as described in Table 8.1-1 Data Collection Schedule and will be summarized using descriptive statistics (e.g., mean, standard deviation, n, minimum, maximum) for continuous variables and frequency tables for discrete variables.

9.3.4. Interim Analyses

No formal interim analyses are planned for this study.

9.3.5. Subgroup Analyses

Stratified analyses will include tabulating the primary and select secondary endpoints by gender.

9.3.6. Justification of Pooling

The analyses will be performed using data pooled across institutions. An assessment of the poolability of patients across sites will be made by fitting generalized linear models with site as the factor of interest and the primary endpoint as the outcome variable.

9.3.7. Multivariable Analyses

Multivariable analyses may be performed to identify potential predictors and assess their effect on the primary endpoint.

9.3.8. Learning Curve Analysis

A generalized linear model will be fit to investigate the effect of time since first enrollment and sites/physicians (and potential interaction between time and sites/physicians) on the primary and select secondary endpoints.

9.3.9. Changes to Planned Analyses

Any changes to the planned statistical analyses made prior to performing the analyses will be documented in an amended Statistical Analysis Plan approved prior to performing the analyses.

10. Data Management

10.1. Data Collection, Processing, and Review

Subject data will be recorded in a limited access secure electronic data capture (EDC) system.

The clinical database will reside on a production server hosted by Medidata Rave. All changes made to the clinical data will be captured in an electronic audit trail and available for review by Boston Scientific Corporation (BSC) or its representative. The associated Rave software and database have been designed to meet regulatory compliance for deployment as part of a validated system compliant with laws and regulations applicable to the conduct of clinical studies pertaining to the use of electronic records and signatures. Database backups are performed regularly.

The Investigator provides his/her electronic signature on the appropriate electronic case report forms (eCRFs) in compliance with local regulations. A written signature on printouts of the eCRFs must also be provided if required by local regulation. Changes to data previously submitted to the sponsor require a new electronic signature by the Investigator acknowledging and approving the changes.

Visual and/or electronic data review will be performed to identify possible data discrepancies. Manual and/or automatic queries will be created in the EDC system and will be issued to the site for appropriate response. Site staff will be responsible for resolving applicable queries in the database.

10.2. Data Retention

The Principal Investigator or his/her designee or Investigational site will maintain, at the investigative site, all essential study documents and source documentation that support the data collected on the study subjects in compliance with ICH/GCP guidelines. Documents must be retained for at least 2 years after the last approval of a marketing application or until at least 2 years have elapsed since the formal discontinuation of the clinical investigation of the product. These documents will be retained for a longer period of time by agreement with BSC or in compliance with other country/regional/local regulations.

The Principal Investigator or his/her designee will take measures to ensure that these essential documents are not accidentally damaged or destroyed. If for any reason the Principal Investigator or his/her designee withdraws responsibility for maintaining these essential documents, custody must be transferred to an individual who will assume responsibility and BSC must receive written notification of this custodial change. Sites are required to inform Boston Scientific in writing where paper or electronic files are maintained in case files are stored off site and are not readily available.

11. Amendments

If a protocol revision is necessary which affects the rights, safety or welfare of the subject or scientific integrity of the data, an amendment is required. Appropriate approvals (e.g., IRB/EC/FDA/CA) of the revised protocol must be obtained prior to implementation.

12. Deviations

An Investigator must not make any changes or deviate from this protocol, except to protect the life and physical well-being of a subject in an emergency. An investigator shall notify the sponsor and the reviewing IRB/EC of any deviation from the investigational plan to protect the life or physical well-being of a subject in an emergency, and those deviations which affect the scientific integrity of the clinical investigation. Such notice shall be given as soon as possible, but no later than 5 working days after the emergency occurred, or per prevailing local requirements, if sooner than 5 working days.

All deviations from the investigational plan, with the reason for the deviation must be documented and reported to the sponsor using the protocol deviation form in the EDC. Sites may also be required to report deviations to the IRB/EC, per local guidelines and government regulations.

Deviations will be reviewed and evaluated on an ongoing basis and, as necessary, appropriate corrective and preventive actions (including IRB/EC notification, site re-training, or site discontinuation/termination) will be put into place by the sponsor.

13. Device/Equipment Accountability

The devices/equipment shall be securely maintained, controlled, and used only in this clinical study. The Device Accountability Log will be used to track subjects and device allocations during the study. Equipment shall be returned in the condition in which it was provided, reasonable wear and tear excepted.

The sponsor shall keep records to document the physical location of all devices/ equipment from shipment of devices from BSC or designated facility/equipment to the investigation sites until return or disposal.

Records shall be kept by the site to document the physical location and conditions of storage of all devices/equipment.

The principal investigator or an authorized designee shall keep records documenting the receipt, use, return and disposal of the devices/equipment, which shall include the following

- Date of receipt
- Identification of each device/piece of equipment (batch number or unique code)
- Expiry date, as applicable
- Date or dates of use
- Subject identification

- Date on which the device/piece of equipment was returned/explanted from subject, if applicable
- Date of return (and number) of unused, expired, or malfunctioning devices/equipment, if applicable.

Written procedures may be required by national regulations.

14. Compliance

